We will measure patient effort of breathing twice daily with esophageal manometry (using Pressure Rate Product [PRP] and Pressure Time Product [PTP]) and once daily using diaphragm ultrasound (using Diaphragm Contractile Activity [DCA]), during the acute and weaning phases in both arms. DCA is obtained by measuring the thickness of the right hemi-diaphragm and calculating the percent difference between diaphragm thickness on inspiration and exhalation. Diaphragm ultrasound measurements will be performed independently by 2 practitioners, one of whom is specifically trained in acute care ultrasound. We will also use ultrasound to measure diaphragm thickness on exhalation and monitor how this changes serially over time as a measure of the architecture of the diaphragm. Finally, we will measure respiratory load (resistance, compliance) daily using spirometry. The clinical team will remain blinded to the results of these measurements in both arms.

D.4.2. Spontaneous Breathing trial respiratory measurements during Airway Occlusion:

Airway Occlusion: Prior to each SBT, we will perform a standardized airway occlusion maneuver to measure neuromuscular capacity with aPiMax (airway) and ePiMax (esophageal), as described in the Preliminary Data. In addition, during airway occlusion we will measure DCA (as above)^{5, 7, 51, 52}, to provide complementary data to PiMax. The clinical team will remain blinded to the results of these measurements in both arms.

D.4.3 Weaning trial measurements during SBTs:

During SBTs, respiratory effort and capacity will be measured with PRP, PTP, inspiratory pressure from esophageal manometry (Pi), Pi/ePiMax, Tension Time Index (TTI), Phase angle (PA), and DCA. Patients will be monitored continuously during the SBT, and all of these measures will be recorded at the beginning of the SBT, and then every 30 minutes (for 5 minute periods) to monitor respiratory muscle endurance over time. The PRP measurements will be shared with the clinical team in both arms because they will be used to help define passage of SBTs (as above). Clinical providers will remain blinded to the results of the other measurements in both arms.

Data Collection timeline	Enrollment	Acute (Daily)	Weaning (Daily)	SBT	Post-Extubation
Demographics (age, race, gender, past medical history, primary diagnoses, comorbidities, PRISM-III-12 severity of illness scores, height, weight, quality of life score)					

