The primary analysis seeks to address if there are differences in length of weaning between: 1) REDvent-acute compared to usual care acute, 2) REDvent-weaning compared to usual care-weaning, and 3) REDvent-acute and weaning (combined) compared to usual care acute and weaning (combined). Analyses of these aims will follow the ITT principle. The primary analyses will compare median weaning duration between groups using a Mann-Whitney U test, or a t-test with transformation as necessary. The effect size (r) will also be computed to assess the magnitude of treatment effect. If imbalances in baseline characteristics are found between or across randomized treatment groups, a Cox proportional hazard model will be performed to adjust for covariates. The estimates (mean, median, or hazard ratio) and the associated 95% confidence interval, as well as the p-values, will be presented for interpretation.

Power analysis: For the primary outcome (weaning duration), a 1-day change in length of weaning is considered clinically significant. It is anticipated that up to 20% of patients may not achieve the primary outcome (successful passage of an SBT or extubation due to death or dropout); these patients will not be included in the primary outcome analysis but will be included in secondary outcomes. We are targeting an overall sample size of 300 patients, with a minimum of 240 patients (120 per arm) available for analysis of the primary outcome. Using the planned statistical tests above, this sample size would be able to detect a ≥ 1 -day change in weaning duration with a two-sided alpha of 0.05 and power of 0.9, or a relative hazard ratio of 1.5 (ratio between control/intervention group) with a power of 0.9 or a hazard ratio of 1.4 with a power of 0.8. Patients who fail the initial SBT will undergo the weaning phase randomization. From our pilot data, approximately 25% of patients exposed to the intervention passed the initial SBT. Anticipating 180 patients (90 per arm) will receive weaning phase interventions, there will be adequate power to detect a ≥ 1 day change in the length of the weaning phase, or a hazard ratio of 1.5 with an alpha of 0.05 and power of 0.8 in the weaning phase.

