The analytic approach for secondary aims and outcomes such as mortality and ventilator free days will follow those described above. For categorical data, a χ^2 or Fisher's exact test will be used to compare difference between groups. Logistic regression will be used to assess binary outcomes, and a multinomial/ordinal logistic regression will be used for categorical outcomes (> 2 categories) while adjusting for covariates. To assess the association between 2 continuous variables, a Pearson or Spearman correlation will be used, and analysis of covariance (ANCOVA) will be used to adjust for covariates. Generalized Estimating Equations (GEE) or mixed effect models will be used when necessary to analyze repeated measures. Because of the physiologic nature of the study with a Phase II design,

multiple comparisons adjustment is not planned for secondary outcomes. Analyses will be performed using the appropriate recent version of the SAS statistical software (SAS Institute Inc., Cary, NC).

In order to increase precision around the effect estimates for the primary and secondary aims and to reflect the stratified sampling, all analyses are adjusted for block randomization variables.³ For acute phase these are age group (infant, child, and adolescent) and whether or not the subject was immunocompromised. For the weaning phase this is acute phase randomization grouping and age group. In addition, variables thought to be potential confounders on the relationship between intervention and outcome with large differences between groups (standardized effect sizes as detailed above) will also be included in all adjusted analyses. Unadjusted analyses will be presented to summarize data; all primary and secondary outcomes will present adjusted analyses controlling for age category, immunosuppression and imbalanced baseline variables. Potential confounders will be assessed for multicollinearity and if present, the confounder with the highest biological plausibility to impact the effect of the intervention on the outcome will be selected for inclusion as a model covariate.

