Model assumptions and fit for multiple linear regression (with or without log transformation) will be assessed visually for normality of residuals as well as variance inflation factor and difference in betas (DFBETAS) for influential points. Model fit for binary multiple logistic regression will be assessed with Pearson Chi-square and deviance. Firth's penalized likelihood method will be used in subgroup analyses when event rates are small to reduce bias in the parameter estimates.⁴ When using negative binomial regression, model fit will be assessed for over and underdispersion with the scaled Pearson Chi-square/deviance and influential points assessed as previously described. The proportional hazards assumption will be assessed when using Cox proportional hazards modeling using graphical approaches ("log-log" figures and Kaplan-Meier curves) for each covariate. Repeated measures analysis for ventilator settings, lung mechanics, and respiratory measures will be assessed with linear mixed models and generalized linear mixed models that include a variable for time from randomization to control for correlation of values within each patient using the first-order autoregressive structure. The robust sandwich estimators for standard errors will be used to reduce heteroscedasticity when appropriate.

A detailed outline of each outcome's analysis approach to control for blocking variables and confounders is given in the Table 1. Pre-specified comparisons of interest are REDvent acute vs. usual care acute, REDvent weaning vs. usual care weaning, and four group combination: 1) REDvent acute + REDvent weaning 2) REDvent acute + usual care weaning 3) Usual care acute + usual care weaning 4) usual care acute + REDvent weaning. The four group combinations comparisons are exploratory and will only be considered if there are noted differences between both acute and weaning phase interventions.

October 2019- new milestone accrual plan

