After the first 75 patients were enrolled in the study a new milestone accrual plan was created to account for the increase in the percentage of patients meeting the primary outcome. Previously, it was assumed 20% of patients would not meet the outcome, however, data after 75 patients revealed this was 13% and the total sample size requirement was adjusted down from 300 to 276 patients. The number of patients targeted per group to meet the primary outcome was unchanged, at 120 per group. This updated milestone accrual plan was reviewed and accepted by the NLHBI and DSMB.

January 2023 - Change in primary analysis for length of weaning

Blinded, non-inferential summary statistics and distributions were assessed for the length of weaning outcome by the primary statistician as part of the data cleaning process. It was revealed that length of weaning might not be optimally analyzed as a continuous variable because SBTs were conducted once a day, with most patients passing their SBT within the first three days. In addition, enrollment had been affected by the COVID-19 pandemic and a new milestone accrual plan was requested by the NHLBI. As the observed distribution appeared more count-like, the primary analysis model was changed to Poisson or Negative binomial regression to better fit the data and satisfy assumptions. This decision was made by the senior biostatistician who was blinded to the randomization groups.

The sample size was re-estimated based on a minimum detectable difference for a reduction in the number of weaning days in the REDvent-acute vs. usual care-acute group using negative binomial regression. This yielded a minimal sample size of 230 patients to detect a reduction of 0.36 to 0.75 days when usual care had an average number of weaning days between 1 and 4, respectively with a power of 80%. This estimate of 230 patients accounted for the 13% loss in those meeting the primary outcome. This updated sample size estimate was reviewed and accepted by the NHLBI and DSMB. Based on this, the milestone accrual plan was revised, and enrollment was planned to continue through March 2024 with a target sample size between 230-276.

May 2024 – Change in primary analysis for length of weaning and PiMax

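### AR(1) is the only within-patient correlation named for the repeated ventilator, mechanics and respiratory measures; fitted alone with model-based standard errors, it lets the arm main-effect test exceed 5%

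*Combined protocol and SAP*

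**What the plan says.** The final SAP (July 2024), in the paragraph on model assumptions and fit, says of ventilator settings, lung mechanics and respiratory measures that they "will be assessed with linear mixed models and generalized linear mixed models". It describes these models as ones "that include a variable for time from randomization to control for correlation of values within each patient using the first-order autoregressive structure". The next sentence reads "The robust sandwich estimators for standard errors will be used to reduce heteroscedasticity when appropriate". Neither sentence lists a random intercept, an alternative covariance, a rule for choosing one, or the contrast to be tested. Earlier in the same SAP there is a general provision: "Generalized Estimating Equations (GEE) or mixed effect models will be used when necessary to analyze repeated measures". The SAP also states that "multiple comparisons adjustment is not planned for secondary outcomes".

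The Fall 2019 SAP has the general provision but not the AR(1) sentence.

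The measurement schedules are in the amended protocol. Section D.4.1 says "We will measure patient effort of breathing twice daily with esophageal manometry" and sets resistance and compliance at once a day. The data collection table sets ventilator settings at every 6 hours.

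**The concern.** A time covariate describes the average trend and does not account for correlation within a child. AR(1) does, but only in a form in which values far apart in time become nearly independent. The children range from infancy to 21 years with varied lung disease, so some are likely to sit persistently high or low. Their correlation then levels off above zero. A model that takes it to be fading credits each child with more independent information than the child supplies, and the standard error of the arm effect is too small.

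At stake are the comparisons showing whether REDvent changed ventilation, effort and mechanics. They are several tests without multiplicity adjustment, and each would carry the same inflation.

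**Working it through.** **No stated figure to reproduce.** The plan gives no error rate, power or correlation for these models. The only benchmark is the nominal level, stated for the primary outcome ("with a two-sided alpha of 0.05 and power of 0.9") and assumed here for the repeated measures.

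**Inputs from the documents.** Median ventilation was 6.5 days with REDvent and 8.4 days in historical controls (protocol B.3.4, Table 1). Taking about 7 days gives 7 × 1 = 7 daily, 7 × 2 = 14 twice-daily and 7 × 4 = 28 six-hourly values. Children may enter up to 72 hours after ventilation starts, so actual counts can be lower, which would reduce the inflation. The final SAP plans enrolment "with a target sample size between 230-276"; the simulation used 240 children, 1:1.

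**Assumptions.** Between-child share of variance (ICC) 0.1, 0.3 or 0.5; lag-1 correlation φ of the within-child part 0, 0.3 or 0.5, with 0.9 as a check.

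**Large-sample formula, total variance 1, n equally spaced values per child.**

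1. The best-fitting AR(1) parameter is ρ = ICC + (1 − ICC)φ.
2. The AR(1) weights are proportional to 1 for the first and last value and 1 − ρ for the others. Their sum is W = 2 + (n − 2)(1 − ρ).
3. Variance of a child's weighted mean according to the model: (1 + ρ)/W.
4. True variance: ICC + (1 − ICC) × w′A(φ)w/W², where w holds the weights and A(φ) is the AR(1) correlation matrix of the within-child part.
5. Type I error = 2 × [1 − Φ(1.96 × SE_model/SE_true)].

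**Example, n = 14, ICC 0.3, φ 0.5.** ρ = 0.3 + 0.7 × 0.5 = 0.65. W = 2 + 12 × 0.35 = 6.2. Model variance = 1.65/6.2 = 0.266. True variance = 0.433. SE ratio = √(0.266/0.433) = 0.784. Type I error = 2 × [1 − Φ(1.536)] = 12.5%.

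**Results for the arm main effect, AR(1) only, model-based SE.**

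| Values per child | ICC 0 | ICC 0.1-0.5, φ 0-0.5 | ICC 0.1-0.5, φ 0.9 |
|---|---|---|---|
| 7 (mechanics) | 5.0% | 6.1-13.7% | 5.1-5.2% |
| 14 (effort) | 5.0% | 8.4-24.8% | 5.3-5.8% |
| 28 (settings) | 5.0% | 13.0-39.0% | 5.8-7.4% |

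The ICC 0 column supposes that the within-child part is exactly AR(1). If 20% of variance is independent measurement noise and φ is 0.7, the rate is 7.5-8.3% at 13-32 values even with ICC 0.

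**Simulation.** No arm effect, unequal follow-up, 200-400 runs per cell, ICC 0.3-0.7 and φ 0.3-0.5; simulation error about ±2 to 3 points.

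| Median values | AR(1), model SE | AR(1), patient-level sandwich SE | Random intercept + AR(1) |
|---|---|---|---|
| 7 | 9-13% | 3.8-6.8% | 2.8-8.0% |
| 14 | 14-21% | 3.0-6.5% | 3.5-6.3% |
| 28 | 28-34% | 4.5-6.5% | not run |

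**Other contrast.** For an arm-by-time slope the direction reverses: with ICC 0.1-0.7 and no measurement noise, AR(1) alone gives 0-5%.

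**The case against.** The strongest reply is that this is an under-specified sentence and not a demonstrated misspecification. A mixed model may carry a random intercept beside an AR(1) residual, and the text neither lists nor excludes one. Sandwich errors appear in the very next sentence, GEE is allowed elsewhere, and either could cure the problem. This stands in part: the inflation arises only if the random intercept is absent and the sandwich errors are not used. But an analyst could follow the specific sentence to the letter and report model-based standard errors, because the safeguard is discretionary, is tied to heteroscedasticity and names no cluster.

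A reader might infer a fixed multiplier, such as two to seven times too many false positives. The documents do not support that. They give no ICC or autocorrelation, daily mechanics fall partly below twofold, and very strong serial correlation almost removes the effect. The planned adjustment for age group, the other stratification factors and imbalanced baseline variables would also lower the residual between-child share by an unknown amount.

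A reader might also infer that different schedules break AR(1). They do not: settings, effort and mechanics are separate outcomes, each with its own regular schedule. Only irregular or missed times within one outcome matter.

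Nor do all claims about effort and settings rest on these models. Protocol D.6.4.1 separately plans to compare time-weighted averages. That is one summary per child, which this problem does not touch.

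**Conclusion.** The point holds conditionally. As written, the SAP permits an analysis in which the arm main-effect test exceeds 5%: about 6-14% for daily mechanics, 8-25% for twice-daily effort and 13-39% for six-hourly settings. These ranges rest on an assumed between-child share of 10-50%, an assumed lag-1 correlation of 0-0.5, about 7 days of measurement, model-based standard errors and no random intercept. Change any of the last three and the size changes; use clustered errors and it returns to about 5%. The documents do not show which analysis was run or which contrast was tested, so they do not support a statement that false differences were in fact declared. The reach is limited to the repeated-measures models: the primary outcome and the other Table 1 outcomes are analysed one value per child.

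**What to change.** State in the SAP that all repeated-measures arm comparisons use sandwich standard errors clustered on patient, without the discretionary qualifier. Preferably add a patient random intercept alongside the serial term, with the serial term based on actual measurement time where values are irregular or missed. Name the contrast tested for each measure: arm main effect or arm-by-time.

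The clustered errors alone restored about 5% in simulation, so they are the essential part; the random intercept is the better description of the data. The cost is a sentence or two in the SAP, a re-run of these models and somewhat wider intervals. If a random intercept or patient-clustered errors were already used, saying so settles the point on standard errors and leaves only the contrast to be named.

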2. Supported on MV for pulmonary parenchymal disease (radiographic evidence of alveolar or interstitial opacifications with a clinical risk factor for lung disease e.g. pneumonia, acute respiratory distress syndrome, aspiration, etc.) with Oxygen Saturation Index (OSI= $(\text{FiO}_2 * \text{Mean Airway Pressure} * 100) / \text{SpO}_2$) ≥ 5 or Oxygenation Index (OI= $\text{FiO}_2 * \text{Mean Airway Pressure} * 100) / \text{PaO}_2$) $\geq 4^1$ AND
3. Within 72 hours of initiation of invasive MV

Exclusion Criteria

1. Contraindications to an esophageal catheter (i.e. severe mucosal bleeding, nasal encephalocele, trans-sphenoidal surgery) OR
2. Contraindications to use of Respiratory Inductance Plethysmography (RIP) bands (i.e. omphalocele, chest immobilizer or cast) OR
3. Conditions precluding diaphragm ultrasound measurement (i.e. abdominal wall defects, pregnancy) OR
4. Conditions precluding conventional methods of weaning (i.e., status asthmaticus, severe lower airway obstruction, critical airway, intracranial hypertension, Extra Corporeal Life Support (ECLS), limitation of care, severe chronic respiratory failure, spinal cord injury above lumbar region, cyanotic heart disease (unrepaired or palliated) OR
5. Primary Attending physician refusal

Randomization Strategy and Blinding

For the acute phase, subjects will be block randomized to either arm in a 1:1 allocation ratio, stratified by age group: infant (30 days -365 days), child (366 days to ≤ 8 years), and older child/ adolescent (9-18 years); and immune suppression (congenital or acquired conditions that result in marked inability to respond to antigenic stimuli). Block randomization will use random block sizes of 4, 6 and 8 within the strata above. Weaning phase randomization is block randomized by acute phase group and age, using the same methodology. Although blinding is not possible given the open label nature of the intervention, analysis will be blinded to treatment groups. Randomization schema was loaded into the central REDCAP database by the unblinded statistician. Patients were consented for the study by one of the study investigators, and randomization in the central REDCAP database was conducted by one of the research respiratory therapists or study investigators. Prior to randomization, blocking strata variables were double checked with a second member of the study team or the primary attending physician.

Statistical Analysis Plan

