Data collection and cleaning were completed at the end of May 2024. During the analysis phase, the unblinded statistician checked assumptions and diagnostics for the primary analysis using negative binomial for outcome length of weaning. During this process two influential outliers were discovered in the usual care group who had attempted a SBT but never had a successful SBT; these two patients remained on IMV at 90 days. These patients were eligible for the primary outcome analysis, so were not removed from analysis, however, they were very influential and biased the estimate for the difference in length of weaning days.

Three sensitivity analyses were proposed to address these outliers: 1) truncate length of weaning to 28 days (instead of 90) using log transformed multiple linear regression, 2) categorize length of weaning into clinically relevant groups and conduct a proportional odds logistic regression model, and 3) revert back to the Cox proportional hazards model and censor patients at 28 days. Each of these sensitivity analyses adjusted for the same blocking variables and confounders used in the pre-specified negative binomial regression model. The truncation approaches failed because the assumptions of both log transformed linear regression and time to event analysis were not met. Residuals were highly skewed in linear regression even after truncation and log-transformation. The PH assumption was violated when adjusting for blocking variables when running the Cox proportional hazards model. The proportional odds logistic regression model categorized length of weaning as follows <0.5 day, 0.5 to <1.5, 1.5 to <2.5, 2.5 to <4.5, 4.5 to <7.5, and \geq 7.5 days. Patients who had a long length of weaning were therefore in the highest category of \geq 7.5 days. The proportional odds model uses a rank-based non-parametric approach to model the probability of a lower ordered value, or in our case, a lower length of weaning which can be thought of a latent continuous variable bucketed into meaningful cutoffs. This model also allowed interpretation of the intervention effect on length of weaning in a stepwise manner, which is more representative of what happens clinically with daily SBTs and does not require that the difference between categories be equal. The proportional odds assumption for each independent variable was assessed graphically using their empirical cumulative logits and overall with the score Chi-square test.⁵⁻⁷

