Because the pre-specified plan was to use a negative binomial model, those findings have been presented in the main results, but because the model does not appropriately fit the data due to the highly influential outliers, the conclusions and abstract results reflect the more appropriate proportional odds model. This model was agreed upon by the study statistical team and DSMB statisticians in June 2024 at the final DSMB meeting.

PiMax was planned to be modeled with linear regression, with truncation of values >100. In the analysis, no transformation could satisfy the assumptions of linear regression, with poor model diagnostics and non-normality of residuals. PiMax was therefore modeled with the proportional odds model given the non-parametric nature of the data. No specific categories were created for PiMax, but instead it was treated as a rank-based variable with comparisons of ranks between groups, adjusting for blocking variables and confounders (oxygenation index). The model allowed us to compare the odds of a higher PiMax ranking for the REDvent vs. usual care groups. Table 1 has been revised and now presents the description of all outcome variables, initial planned analyses, and modifications to initial proposed analyses and the timing of those changes. In addition, since all outcomes are presented as adjusted analyses, Table 2 details the four main modeling approaches used in these analyses, and interpretation of the model intervention parameter estimates.

References

1. [name] RG, Smith LS, Zimmerman JJ, et al. Pediatric Acute Respiratory Distress Syndrome: Definition, Incidence, and Epidemiology: Proceedings From the Pediatric Acute Lung Injury Consensus Conference. *Pediatric Critical Care Medicine*. Jun 01 2015;16(5_suppl):S23-S40. doi:10.1097/PCC.0000000000000432
2. [name] RG, Hotz JC, Klein MJ, et al. A Phase II randomized controlled trial for lung and diaphragm protective ventilation (Real-time Effort Driven VENTilator management). *Contemp Clin Trials*. Jan 2020;88:105893. doi:10.1016/j.cct.2019.105893
4. Firth D. Bias Reduction of Maximum Likelihood Estimates. *Biometrika* 1993. p. 27-38.

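### The primary conclusions rest on six weaning-time categories that first appear in May 2024, after an unblinded look at the data; the uncollapsed model should be reported beside them.

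*Combined protocol and SAP*

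**What the plan says.** All references are to the final SAP (July 2024) unless stated.

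- **The trigger.** The section on the May 2024 change says that "During the analysis phase, the unblinded statistician checked assumptions and diagnostics for the primary analysis using negative binomial for outcome length of weaning". Two influential outliers came to light, both in usual care and both still ventilated at 90 days.
- **The response.** Three sensitivity analyses were proposed. Two were dropped on diagnostics: log-linear regression for skewed residuals, and Cox for non-proportional hazards. The third was to "categorize length of weaning into clinically relevant groups and conduct a proportional odds logistic regression model". It "categorized length of weaning as follows <0.5 day, 0.5 to <1.5, 1.5 to <2.5, 2.5 to <4.5, 4.5 to <7.5, and" a top group of 7.5 days or more.
- **Its status.** Negative binomial, which the SAP calls its pre-specified model, stays in the main results, but "the conclusions and abstract results reflect the more appropriate proportional odds model". The study's statisticians and the DSMB statisticians agreed to this in June 2024.
- **PiMax.** The same section moves PiMax to proportional odds and says: "No specific categories were created for PiMax, but instead it was treated as a rank-based variable".
- **The primary test elsewhere.** The Statistical Analysis Plan section still reads "The primary analyses will compare median weaning duration between groups using a Mann-Whitney U test", with a transformed t-test as the alternative. Table 1 gives Cox as the initial approach. The January 2023 change, made by a biostatistician blinded to groups, substitutes Poisson or negative binomial.
- **Blinding.** Randomization Strategy and Blinding states that "analysis will be blinded to treatment groups".

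**The concern.** The cut-points are an analysis choice that first appears after someone with access to the arms had examined the primary outcome. They are in neither the Fall 2019 SAP nor the January 2023 change. They are also missing from the May 2024 entry in Table 1, from Table 2 and from the summary of changes. They are described as clinically sensible, without a source. The January 2023 change says who decided and that this person was blinded; the May 2024 text says neither about the cut-points.

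If the cuts could have been chosen with results in view, the headline p-value and interval cannot be shown to be free of selection. That matters most for a borderline result. A second consequence concerns scale: the headline is an odds ratio, whereas the SAP's clinical threshold is a 1-day change, so the headline alone cannot be read against it.

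**Working it through.** **1. The plan's own figure.** The SAP states power of 0.9 for a 1-day change with 120 per arm and two-sided alpha of 0.05. The protocol gives SDs of 2.1 and 2.8 days.

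Power = Φ(Δ / (SD·√(2/n)) − 1.96)

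- Mean SD 2.45: 2.45 × √(2/120) = 0.316; 1/0.316 = 3.16; Φ(1.20) = 0.885.
- Pooled SD √((2.1² + 2.8²)/2) = 2.475: Φ(1.17) = 0.879.

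The stated figure is close to what its inputs give. It concerns a difference in days, which the headline model does not estimate.

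**2. Why two values upset a model for means but not ranks.** The revised minimum of 230 with 13% not evaluable leaves 230 × 0.87 ≈ 200, or 100 per arm. The SAP assigns 90 days to a child still intubated at day 90.

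- *Effect on the usual-care mean:* 2 × 90 / 100 = 1.8 days (1.5 days with 120 per arm), more than the 1-day threshold.
- *Effect on ranks:* two children enter 2 × 100 = 200 of 100 × 100 = 10,000 between-arm pairs, or 2%, whether their value is 90, 28 or merely the largest.

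In simulation, truncating at 28 instead of 90 days left the uncollapsed rank test unchanged. The categories therefore add nothing to the handling of these two values.

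**3. What the cuts correspond to.** The protocol (D.3.4) holds SBTs daily between 9 and 11 AM, and Table 1 puts a first-SBT pass at about 2 hours (0.083 day). Later passes on schedule fall near 1.08, 2.08, 3.08 days and so on. Cuts at 0.5, 1.5 and 2.5 separate consecutive daily trials. Cuts at 4.5 and 7.5 group several days together, and here there is real discretion.

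**4. Type I error and power.** The documents hold no outcome data, so every distribution below is assumed. The test is Mann-Whitney with midranks, the score test of an unadjusted proportional odds model. The fixed-category, best-of-7 and power rows use 100 per arm, daily geometric passage after the first SBT, and two children at 90 days.

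| Check | Uncollapsed | Categorised |
|---|---|---|
| Null, 25% pass first SBT, six fixed categories | 0.049 | 0.046 |
| Null, 50% pass first SBT, six fixed categories | 0.052 | 0.051 |
| Null, smallest p from 7 cut-point sets (25%; 50%) | as above | 0.074; 0.066 |
| Null, 216 children, about 28% pass first SBT, smallest p from 8 sets | 0.054 | 0.106 |
| Null, 216 children, cuts 0.5/1.5/2.5 held, smallest p from 9 upper-cut sets (83%; 91% weaned by about day 3) | 0.049; 0.056 | 0.057; 0.061 |
| Power, first-SBT pass 25% v 40%, six fixed categories | 0.829 | 0.830 |
| Power, first-SBT pass 50% v 62%, six fixed categories | 0.520 | 0.525 |

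The 100-per-arm null rows use 2,500 trials each, so the Monte Carlo standard error near 0.05 is √(0.05 × 0.95 / 2500) = 0.004. A further run gave 0.06 to 0.10 for the best of 8 free cut-point sets and 0.05 to 0.06 when only the upper cuts varied. Across all runs, the six categories and the uncollapsed ranks fell on opposite sides of 0.05 in about 1% to 4% of trials.

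The smallest-p rows are upper bounds: they assume that the cuts were picked to minimise p.

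**The case against.** The strongest defence has four parts, and much of it stands.

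- **The change is disclosed and reviewed.** It is dated, the negative binomial result stays in the main results, the rejected alternatives have stated reasons, and the DSMB statisticians agreed. This is good practice. It does not show that the cut-points were set without knowledge of results.
- **The lower cuts follow the daily SBT schedule.** This stands, and it narrows the discretion mainly to 4.5 and 7.5 days.
- **The direction does not obviously favour REDvent.** Both outliers are in usual care, so limiting them removes values that lengthen the usual-care mean. This stands for the point estimate. Outliers also add dispersion, so the net effect on the p-value cannot be read from the documents.
- **The missing figure in days was not caused by the categories.** This stands: a hazard ratio and then a rate ratio were planned before. It remains a reporting gap against the 1-day threshold.

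A reader might infer that the SAP's real primary test was rank-based and was abandoned. The documents do not support that. The sentence naming Mann-Whitney also allows a t-test and is carried over from Fall 2019; Table 1 says Cox; and negative binomial was the operative plan from January 2023. A plain Mann-Whitney test would also not give the adjusted analysis that the SAP requires. What stands is that these statements conflict.

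**Conclusion.** The point holds as one of robustness and documentation. The conclusions use cut-points that first appear after an unblinded look, that are not needed for the problem they were meant to solve, and whose author and basis are not recorded. Taken as fixed, the six categories are sound: alpha near 0.05 and no loss of power. The exposure is selection of the cuts. Its upper bound is type I error of about 0.05 to 0.06 if only the upper cuts were open, and up to about 0.10 if all were. These figures rest on assumed weaning-time distributions and on an unadjusted test.

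Two stronger readings go beyond the documents. One is that the cuts were chosen knowing the arms or the effect. The May 2024 text says only that the unblinded statistician found the outliers; an unblinded statistician existed from the start, to load the randomisation schedule. The other is that error is inflated further by also counting the log-linear and Cox fits as candidates for selection. The SAP rejects those on model diagnostics, and nothing shows that they were screened by p-value.

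**What to change.** 1. In the May 2024 section and Tables 1 and 2, add the proportional odds model on uncollapsed length of weaning, adjusted for the same blocking variables and confounders. Report it beside the six-category and negative binomial results. Require the conclusion to hold under the uncollapsed fit, or state that it depends on the cut-points. Co-reporting is preferable to replacing the headline, which would be another post-hoc switch.
2. Label the six categories post hoc. State who set them, when, on what basis, and whether results by arm had been seen. Settle the timing too: the summary of changes says April/May 2024, while the text places the work after data cleaning ended in late May.
3. Report a between-arm difference in days, for example restricted mean weaning days to day 28 with a confidence interval, to be read against the 1-day threshold.
4. Reconcile the Mann-Whitney or t-test sentence with Table 1, the January 2023 change and the statement that negative binomial was pre-specified. Reconcile the blinded-analysis statement with the unblinded diagnostics.

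The cost is one extra model and a few lines of reporting, with no new data. In the simulations the uncollapsed analysis lost no power.
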